Cover Page

Title: Improving Social Interaction for Adolescents with Autism During the Transition to Adulthood

NCT Number: NCT03785327

Document Date: 7/2018

Methodology

Participants

In total, we are aiming for 154 participants ages 18 to 21 to be tested interacting in pairs of one autistic and one non-autistic participant. Participants are assigned to one of three conditions:

1. The “neurostimulation” group with 22 autistic and 44 non-autistic adolescents. The autistic participants complete two sessions with different non-autistic participants at least one week apart, once with active neurostimulation preceding the social interaction, and once with sham neurostimulation in order to rule out placebo effects. This group allows for evaluation of Goal 2.
2. The “inclusion training” group with 22 autistic and 22 TD adolescents. Each non-autistic participant receives inclusion training prior to the interaction. Comparing outcomes with the “no intervention” group allows for evaluation of Goal 3.
3. The “no intervention” group consists of 22 autistic and 22 non-autistic adolescents. This group allows for evaluation of Goal 1 and also serves as a baseline for comparison with the intervention groups.

All participants will be male and between 18 and 21 years old. There is a disproportionate male to female ratio in autism of 4:1 (Fombonne, 2009), and the recruitment source used for this study is over 80% male. Thus, we would not have enough female participants to assess gender effects and because social interaction likely differs between mixed-sex interactions relative to same-sex ones, including a handful of females would confound reported findings. All included autistic participants will have a composite score above the clinical threshold for ASD on the Autism Diagnostic Observation Schedule (ADOS-II; Lord et al., 2012). Non-autistic participants will have no history of psychiatric illness or developmental disabilities and no current ASD diagnosis or a first degree relative with an ASD diagnosis. Interaction partners within and across the three groups will be matched on age and race, and comparable on IQ. To control for effects of intellectual ability, and to ensure results are most relevant to autistic older adolescents without intellectual disability, all participants will have measured full-scale IQs over 80 to ensure they are in the average to above average range.

Autistic participants will be recruited from the Autism Research Collaborative at UT Dallas, a database established by [name] of over 150 local autistic adolescents and young adults who have consented to participate in research studies at UTD. Individuals in this database have been clinically evaluated previously and satisfy the eligibility requirements for participation in this study. Non-autistic adults will primarily be students at UT Dallas participating to receive course credit, as well as a database of students who have consented to be contacted to participate in paid research. Data collection will occur in [name] laboratory at UT Dallas, or at the nonPareil Institute, a non-profit organization for autistic adults in Plano, Texas that has partnered with [name] for research studies and provides his lab group with space for testing.

Procedures

Participants are screened prior to data collection to rule out exclusion criteria, answer demographic questions, determine scheduling availability, and ensure unfamiliarity with their potential interaction partner. Testing rooms will have two chairs positioned opposite each other for the social interaction, and a video camera will be set up to capture both participants' full bodies in the frame. Chairs will be angled in such a way that faces are clearly visible to the video camera. After the informed consent process, participants will complete a videotaped unstructured measure of dyadic interaction, first developed for interactions between non-autistic individuals (Berry & Hansen, 1996) but recently used in autism (Usher et al., 2018). Participants will be seated opposite from each other in front of a video camera and instructed that they will have five minutes to get to know each other. The research assistant then will turn on the camera and set a timer for five minutes. Although the researcher will be present during the conversation to ensure participants complete the interaction, he or she will be separated from the participants using a partition.

Measures

Following the interaction, participants will complete measures at separate computer stations partitioned from each other using Qualtrics Survey software. These measures include:

1. *The Social Interaction Evaluation Measure* (Berry & Hansen, 1996): assesses each partners' evaluation of interaction quality (e.g., enjoyment of the interaction), disclosure (e.g., how much did your partner disclose in the conversation), engagement (e.g., how much did your partner influence the conversation), and intimacy (e.g., to what extent was the interaction intimate).
2. *First Impression Scale* (Sasson et al., 2017): participants rate their partner on different traits (e.g., likeability and intelligence) and their intent to engage in future interactions.
3. *The Subjective Closeness Index* (Berscheid et al., 1989) and *the Inclusion of the Other in the Self* (Aron et al., 1997): participants rate feelings of "closeness" to their partner, which is predictive of friendship formation of two unfamiliar partners and can be reliably detected even in brief interactions (Aron et al., 1997).

For items 1 and 2 above, participants will also report how they expect they will be rated on these items by their partner. We have shown that young autistic adults are often less accurate at determining how they are viewed by others (Sasson et al., 2018), an important skill for managing social relationships. We predict here that older autistic adolescents will not only be rated more poorly by their non-autistic partner than vice versa, but that they also will be poor at detecting they are being evaluated in this way. The neurostimulation intervention that targets areas of the brain involved in perspective-taking is predicted to improve this ability in our autistic participants. In contrast, the inclusion training is predicted to improve non-autistic impressions of autistic participants, but not affect autistic behavior or responses.

Participants also complete measures assessing their social cognitive and social motivation abilities, as these affect social behavior and often differ in autism:

1. *Penn Emotion Recognition Task* (Kohler et al., 2000): assesses the ability to recognize five basic emotions (i.e., happiness, sadness, fear, anger, and no emotion) from facial expressions.
2. *Benton Facial Recognition Task* (Benton et al., 1983): measures the ability to process facial identity.

3. *The Awareness of Social Inference Task* (TASIT; MacDonald et al., 2003): participants will view 16 videotaped vignettes of social interactions involving white lies or sarcasm and are asked to answer questions about what the characters' intentions and motivations.
4. *Friendship Motivation Scale* (Richard & Schneider. 2005): a 12-item questionnaire that assesses the participant's desire to seek out and form social relationships.

Analytic Plan

Sample sizes were selected in consultation with Statistician [name] to ensure successful detection of the anticipated medium effect sizes with 80% power. The research team consists of established researchers who are well experienced in data analysis and interpretation. For this project, we have selected an analytic approach designed to evaluate our three primary research goals. First, all self-report questionnaires will be evaluated for internal consistency using Cronbach's alpha, and the Conversation Probe social behaviors will be evaluated with Intraclass Correlation Coefficients (ICC) for agreement between coders. In addition to reliability, descriptive statistics will be run for all measures, examining group means, standard deviations, and normality of all measures.

Next, all primary goals will be assessed using an "Actor Partner Interdependence Model" (APIM; Kenny, Kashy, and Cook, 2006). Because data will be collected on two interacting individuals, the primary outcomes for both partners will be related (i.e., interaction evaluations, closeness, and impressions are dependent on the interaction with the partner). Thus, outcomes will be non-independent, and traditional analytic techniques using the general linear model cannot be used. Additionally, hypotheses examining how the partners influence each other cannot be examined with these traditional techniques and instead must be modeled with analyses like the APIM that take non-independence into account. APIM can estimate three types of effects. First, APIM can specify actor effects, or the effect of the individual's own behavior (e.g., overall social skills or social cognitive ability) on the individual's own outcome (e.g., interaction quality). Second, these models can specify partner effects, or the effect of the partner's behaviors or abilities on the individual's outcome. Finally, this model can specify interaction effects, allowing for examination of how an individual's behaviors and traits are related to his own outcomes depending on his partner's behaviors and traits.

To examine effects of autism acceptance training on non-autistic participants interaction with autistic partners, zero-order correlations between participants' interaction ratings were evaluated to assess the relationship between indicators, as well as the consistency of ratings between partners. Two factor mixed-model ANOVAs were run using a Geisser-Greenhouse correction to assess the effects of diagnosis (autistic vs. non-autistic) and training condition (Autism Acceptance Training vs. control) on how participants evaluated their conversation partner and the overall interaction. Specifically, training condition was treated as a between-subjects variable and autistic and NA interaction ratings (interaction quality, first impressions, closeness, warmth and dominance) were treated as a within-subjects factor, with separate analyses run for each outcome measure. As IQ differed significantly between autistic and NA individuals within dyads, WRAT-3 scores were included as a covariate in each ANOVA. All analyses were completed using SPSS 27 (IBM SPSS Inc., 2015).

All analyses addressing each of the three goals will be conducted separately for each social interaction outcome: social interaction evaluation, closeness, and first impressions formed (i.e., traits and behavioral intentions). Analyses for goal 3 (the “no intervention” condition) will serve as a baseline to compare effectiveness of the neurostimulation intervention (goal 1) and the inclusion training (goal 2). Compared to baseline, it is anticipated that neurostimulation of autistic participants will lead to increased evaluation of their social skill, better performance on social cognitive tasks, and higher ratings by their non-autistic partners on closeness and first impressions. Both partners in the neurostimulation condition are predicted to rate the quality of the social interaction higher than in the baseline condition. Goal 2 (inclusion training for the non-autistic participant) is predicted to lead to higher ratings of closeness and first impressions made by non-autistic participants of their autistic partners, with both partners evaluating the social interaction more positively compared to the “no intervention” condition. Because inclusion training only targets the non-autistic individual, social skill and social cognitive performance of autistic participants is not expected to differ here compared to baseline. Finally, we will be able to compare effects between Goal 1 and Goal 2 to determine which intervention, neurostimulation or inclusion training, produces better social outcomes for autistic adolescents. Due to the number of tests that will be performed, all significance tests will be evaluated at an adjusted alpha threshold of .01.

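### The training ANOVA drops a whole dyad when one rating or covariate is missing, and the plan has no rule for a missed second session in the one group that has two visits

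*Combined protocol and SAP*

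**What the plan says.** **Groups and visits (Methodology, Participants).** The plan states "we are aiming for 154 participants ages 18 to 21 to be tested interacting in pairs". The neurostimulation condition is a "group with 22 autistic and 44 non-autistic adolescents", and its visit structure is "The autistic participants complete two sessions with different non-autistic participants at least one week apart", one session active and one sham. The inclusion-training condition is a "group with 22 autistic and 22 TD adolescents", and "The “no intervention” group consists of 22 autistic and 22 non-autistic adolescents". One interaction per dyad is described for these two groups.

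**Primary analysis (Analytic Plan, actor-partner paragraph).** All primary goals are assigned to an Actor Partner Interdependence Model (APIM). The reason given is that partners' outcomes are dependent and that conventional general-linear-model techniques are therefore unusable. The estimation method and the treatment of incomplete dyads or sessions are not given.

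**Training analysis (Analytic Plan, training paragraph).** Here the method is a two-factor mixed ANOVA with a Geisser-Greenhouse correction: "training condition was treated as a between-subjects variable and autistic and NA interaction ratings" are the between and within factors. WRAT-3 is a covariate, each outcome has its own ANOVA, and the software is SPSS 27. The paragraph is in the past tense.

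**Comparisons (Analytic Plan, last paragraph).** The neurostimulation group is compared with the no-intervention group ("Compared to baseline, it is anticipated that neurostimulation of autistic participants will lead to increased evaluation of their social skill") and with inclusion training. The alpha level is .01.

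The document defines no analysis set, attrition allowance, replacement rule, or handling of missing forms or sessions.

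**The concern.** There are two separate issues.

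1. **Incomplete dyads in the training analysis.** A repeated-measures ANOVA with the two partners as the repeated factor has one record per dyad. A record with one rating or the covariate missing is not used. The partner who did respond is lost as well, which costs precision. If non-response is related to how the conversation went, it can also bias the training effect. The choice also departs from the plan's own argument for an APIM. Training is one of the three goals under either of the goal numberings the plan uses, so it falls within that argument.

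2. **A return visit in one group only.** Neurostimulation participants can be lost between sessions; the other groups cannot. Loss related to the outcome would not cancel in the comparisons with the no-intervention and training groups, because those groups had no second visit to miss. With no analysis set defined, an analyst could keep or discard a lone first session, and could make that choice after seeing the data.

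**Working it through.** **Step 1. Reproduce the planned total.** From Participants: 22 + 44 + 22 + 22 + 22 + 22 = 154, which matches the plan. The 44 neurostimulation partners equal 22 × 2 sessions, so the count assumes that everyone returns and holds no reserve.

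**Step 2. What the ANOVA does with an incomplete dyad.** The between factor is training condition, the within factor is partner role, and the case is the dyad: 22 + 22 = 44 dyads and 88 ratings per outcome. The SPSS procedure is not named. The Geisser-Greenhouse correction belongs to the classical repeated-measures ANOVA, which uses complete cases only.

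**Step 3. Dyads lost.** The documents give no missing-data rate, so the rates below are assumptions, with missingness independent between partners. If each rating is missing with probability q:
- share of dyads dropped = 1 − (1 − q)²
- valid ratings discarded = 88 × q × (1 − q)

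| q (assumed) | Dyads dropped | Of 44 | Valid ratings discarded |
|---|---|---|---|
| 2% | 4.0% | 1.7 | 1.7 |
| 5% | 9.8% | 4.3 | 4.2 |
| 10% | 19.0% | 8.4 | 7.9 |

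If the same dyads tend to miss both forms, fewer dyads are dropped for the same q. Missing WRAT-3 values would add to the loss.

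**Step 4. What that costs in power (illustration).** Take the role-by-condition interaction with f = 0.25, within-dyad correlation ρ = 0.5 and alpha .01. The first two are assumptions; the plan says only that effects are medium. The noncentrality is λ = f² × 2N / (1 − ρ) and the test is F with 1 and N − 2 degrees of freedom.
- N = 44: λ = 0.0625 × 88 / 0.5 = 11.0, power 73%
- N = 40: λ = 10.0, power 67%
- N = 36: λ = 9.0, power 61%

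These show the cost of losing dyads entirely. A model that keeps the valid rating recovers part of that cost, not all of it.

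**Step 5. The second visit.** Assumed non-return of 5%, 10% or 20% of 22 leaves 20.9, 19.8 or 17.6 participants with both sessions. Only if the analysis were restricted to completers would the first-session forms of the others (two per dyad) be discarded: 2.2, 4.4 or 8.8 forms. For a paired active-versus-sham test with a standardised difference of 0.5 at two-sided alpha .01 (sidedness assumed), power would go from 34% with 22 pairs to about 32%, 29% or 25%.

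**Step 6. A first-session-only comparison.** If order is balanced (not stated), about 22 / 2 = 11 neurostimulation dyads have their active session first. Against 22 no-intervention dyads, with d = 0.5 and a two-sided t test, power is about 26% at .05 and 10% at .01. This can serve only as a sensitivity analysis.

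**The case against.** **The neurostimulation sentence is not a completer rule.** A reader might infer that the 22 are by definition people who came back, so that a non-returner's data are removed. The text does not support this. It gives a recruitment target and describes a two-session design; it sets no analysis set or replacement rule. An APIM fitted by likelihood could keep a lone session, and no complete-pair analysis is specified for this group. This objection stands: on this part the plan is silent, not wrong.

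**Direction and size of bias.** A reader might also infer that selective return favours neurostimulation by a large fraction of a medium effect. That requires the lowest scorers to be the ones who leave, which is a worst case. If the active session came second, with a different partner, selection on the first session would carry over only through the correlation between sessions. Discomfort with stimulation need not track conversation ratings. This stands too, and no direction or size is claimed here.

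**Few forms will be missing.** Procedures and Measures have both partners completing forms on site, at computer stations, after a five-minute conversation, and scheduling availability is screened beforehand. This makes the low end of the Step 3 range more likely. It does not change what the ANOVA does with an incomplete dyad.

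**The issues are distinct.** Between-visit loss cannot affect the training ANOVA, since both of its groups have one interaction. They share only a remedy.

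**Conclusion.** The point holds for the training analysis as a property of the stated method: an incomplete dyad is dropped whole for that outcome. This rests on the classical SPSS repeated-measures procedure having been used, as the description indicates. The analysis also departs from the plan's own assignment of all primary goals to an APIM. The loss is probably small: about 4% to 19% of 44 dyads if 2% to 10% of ratings are missing independently, with the lower end more likely.

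For the neurostimulation group, the finding is an unfilled gap in the one group exposed to between-visit loss. The plan neither requires nor prevents a completers-only analysis. Without stated attrition or active/sham order, the size and direction of any bias cannot be determined. The stated 80% power is not challenged here.

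The change is worth making because it is cheap and settles the choice in advance wherever analysis has not yet been done.

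**What to change.** 1. **Model.** Replace the complete-dyad ANOVA with a likelihood-based dyadic mixed model in APIM form, and use the same form for every condition contrast. Use one row per rater per session, with effects for dyad and for autistic participant. Fully observed, that is (44 + 22 + 22) × 2 = 176 rows per outcome. State the estimation method, and state how a missing WRAT-3 value is handled, since a mixed model still drops a row whose covariate is missing.
2. **Analysis set.** Include every autistic participant who starts session 1, with all sessions obtained. If a non-returner is replaced to reach 22, keep the original session-1 dyad in the analysis.
3. **Reporting.** Give missing ratings and missed sessions by group and session, and non-returners by first-session condition (active or sham).
4. **Sensitivity.** If first-session dyads are compared with the no-intervention group, label that as a low-power sensitivity analysis.

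**Cost.** The plan needs new wording and slightly more modelling, with no added participants or procedures. The active and sham sets will not be perfectly paired. The training paragraph reads as work already done; if so, the change there is a re-analysis, and the report should say that it was made afterwards.

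### The between-condition contrasts neither match on nor adjust for the autistic partner's ADOS score, although it is held for all 66 autistic participants before any intervention

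*Combined protocol and SAP*

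**What the plan says.** **Score and timing.** Methodology, Participants makes the ADOS-II an entry criterion: "All included autistic participants will have a composite score above the clinical threshold for ASD on the Autism Diagnostic Observation Schedule". The recruitment paragraph that follows says of the source database: "Individuals in this database have been clinically evaluated previously and satisfy the eligibility requirements for participation in this study". The score therefore precedes any intervention.

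**Allocation and matching.** The same Participants section says: "Participants are assigned to one of three conditions". It describes neither randomisation nor stratification. On balance between groups it says: "Interaction partners within and across the three groups will be matched on age and race, and comparable on IQ". ADOS is not in that list.

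**Group sizes.** Inclusion training is a "group with 22 autistic and 22 TD adolescents". The no-intervention "group consists of 22 autistic and 22 non-autistic adolescents". Neurostimulation has 22 autistic participants, each seen once under active and once under sham stimulation.

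**Covariates.** In the Analytic Plan, the paragraph on acceptance training says: "WRAT-3 scores were included as a covariate in each ANOVA". The reason given is that IQ differed between the two partners within dyads. The Actor Partner Interdependence Model (APIM) paragraph mentions individual characteristics only as illustrations ("e.g., overall social skills or social cognitive ability"). The closing paragraph, which sets out the comparisons with no intervention and between the two interventions, names no covariate.

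**The concern.** Several outcomes are a stranger's impression of an autistic person, and the closeness felt to him, after five minutes of conversation. How marked that person's autistic social presentation is could plausibly predict those ratings. The plan's own reasoning points the same way: it expects autistic partners to be rated less favourably, and it proposes to model how one partner's abilities affect the other's outcome.

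ADOS is the only autism-specific measure the documents name that is taken before intervention. If severity differs between two groups of 22, that difference enters the contrast. If severity predicts the outcome, the variance it explains stays in the error term.

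The social-cognition tasks given after the interaction are not a clean replacement. The plan predicts that neurostimulation will improve them, so adjusting for them could remove part of the effect under study.

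**Working it through.** **Inputs from the documents.** 22 autistic participants per condition; alpha .01; a medium effect with 80% power, with no numerical effect size given.

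**Assumptions.** Medium means d = 0.5 (outcome SD 1); tests are two-sided; r, the ADOS-outcome correlation, runs from 0.2 to 0.5. The documents give no value for r.

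**1. The plan's own figures.** The total reproduces: 22 + 44 + 22 + 22 + 22 + 22 = 154. The 80% power cannot be checked in full, because the numerical effect, the alpha used for sizing and the within-dyad correlation are not given. A plain 22 vs 22 comparison at d = 0.5 (noncentral t, 42 df) has power 36.7% at two-sided .05 and 16.3% at two-sided .01. A 2 x 2 mixed-ANOVA interaction with f = 0.25 and an assumed within-dyad correlation of 0.3 gives 78.2% at .05 and 54.6% at .01.

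**2. Size of a chance imbalance, if assignment were random.** The SE of a standardised difference in mean ADOS is sqrt(2/22) = 0.3015.
- P(|difference| > 0.3 SD) = 2 x [1 - Phi(0.3/0.3015)] = 32%.
- P(|difference| > 0.5 SD) = 2 x [1 - Phi(0.5/0.3015)] = 10%.
- 95% range: +/- 1.96 x 0.3015 = +/- 0.59 SD.

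**3. Shift in an unadjusted contrast.** Shift = r x imbalance.

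| Imbalance | r = 0.2 | r = 0.3 | r = 0.5 |
|---|---|---|---|
| 0.30 SD (one SE) | 0.06 | 0.09 | 0.15 |
| 0.50 SD | 0.10 | 0.15 | 0.25 |

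**4. Precision gained by adjustment.** The residual variance is 1 - r², so the standardised effect becomes 0.5/sqrt(1 - r²) and the equivalent group size 22/(1 - r²). Power is from the noncentral t with 41 df (42 unadjusted) at two-sided .01. The last column also charges the average cost of estimating the slope when ADOS differs by chance between groups. This multiplies the variance by 1 + 1/(44 - 4) = 1.025.

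| r | Variance removed | Equivalent n per group | Power | Power with slope cost |
|---|---|---|---|---|
| unadjusted | - | 22 | 16.3% | - |
| 0 | 0% | 22.0 | 16.3% | 15.8% |
| 0.2 | 4% | 22.9 | 17.1% | 16.6% |
| 0.3 | 9% | 24.2 | 18.2% | 17.7% |
| 0.5 | 25% | 29.3 | 23.0% | 22.4% |

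**5. Steps 3 and 4 overlap under random assignment.** The unadjusted contrast has variance 2/22 = 0.0909. The share due to chance differences in ADOS is r² x 0.0909, for example 0.25 x 0.0909 = 0.0227 at r = 0.5. Its square root is 0.15, the one-SE entry in step 3. The chance imbalance and the avoidable noise are then one quantity, not two harms. They separate only if assignment is systematic, when the shift in step 3 is a bias that the standard error does not cover.

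**The case against.** **No imbalance is shown.** A reader might infer that the conditions do differ in severity. The documents give no ADOS distribution by condition, so this is a risk only. The objection stands.

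**Chance imbalance is not bias.** A reader might take the 0.10-0.25 SD shift in step 3 as a bias of 20-50% of the planned effect. That joins an imbalance with a 10% probability to an assumed r. Under random assignment it is already in the standard error, and the .01 test keeps its level. This stands for random assignment, but random assignment is not described. If allocation were systematic, the undefined allocation would be a separate defect, and one covariate would not cure it.

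**The gain may be very small.** All autistic participants are above the ADOS threshold, male, 18-21 and with IQ over 80. This restriction may lower r, and at r = 0.2-0.3 the gain is at most about two power points. This stands.

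**The two-sample calculation is a simplification.** Both partners provide ratings, and the ANOVA treats partner role as a within-dyad factor. For the diagnosis-by-training term, ADOS helps only if it predicts the difference between the partners' ratings. The figures also leave out WRAT-3. They therefore show the scale and are not a power statement for the planned models.

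**Individual differences are already considered.** The APIM paragraph names social skills and social cognitive ability, but only as examples. For inclusion training the plan expects no change in the autistic partner's social cognition, so those measures are less problematic there. For neurostimulation they remain unsuitable. The planned descriptive statistics for all measures may already include ADOS, though the plan does not say so.

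**The training analysis is written in the past tense.** This affects how an added covariate should be labelled, not whether it is useful.

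**Conclusion.** The point holds as a modest improvement to the three between-condition contrasts. A pre-intervention severity score is held for every autistic participant and appears in neither the matching list nor any named covariate set. With 22 per group and no randomisation described, a chance or systematic severity difference would go uncorrected.

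On the assumptions of d = 0.5, two-sided .01 and a simple two-group model, adjustment moves power from about 16% to about 17-18% at r = 0.2-0.3, and to about 22-23% at r = 0.5. A reader might infer that adjustment would rescue the sample size; it does not come near 80%. The better reason to act is protection against imbalance at almost no cost.

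A reader might also extend the point to every comparison of conditions. It does not apply to active vs sham, where each autistic participant is his own control.

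**What to change.** In the Analytic Plan, for the APIM, the ANOVAs and the closing paragraph on comparisons, add wording such as: *Every between-condition model includes the autistic partner's ADOS composite, centred, as a dyad-level covariate alongside WRAT-3. The covariate set is the same for all outcomes and is not chosen by significance tests of group differences. ADOS scores are tabulated by condition.*

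If the diagnosis-by-training interaction is to be adjusted as well, the ADOS term must be crossed with partner role, because a term common to both partners cancels from their difference.

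Where the training analysis has already been run, report the ADOS-adjusted version as a sensitivity analysis beside the original. Terms for age and race are optional: both are matched on, and no gain from adding them has been shown.

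**Cost.** The change needs SAP wording, one table row and one error degree of freedom (a further within-dyad one if the term is crossed with role), using data already held. If ADOS proves unrelated to the outcome, power in the simple two-group model falls from 16.3% to about 15.8% once the average slope cost is counted.
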